# 4. Study design

A prospective, single arm, open-labelled clinical study

#### 5. Sample size

For an assumed efficacy of 90%, a sample size of 138 participants is needed for the study in three study sites for +/- 5% precision (this is width = 0.1 in document), i.e., 85 to 95%. Allowing for a 5% drop out, we propose a sample size of 145 patients for the three study sites in three western provinces of Pailin, Battambang and Pursat.

#### 6. Study population

The study will be conducted at Pailin and Pursat in western Cambodia and Tasanh Health Centre, Samlout District, Battambang. Khmer patients will be recruited from the surrounding areas using a network of Volunteer Malaria Workers and by active case detection, prescreening febrile patients with a malaria rapid diagnostic test before referral to the hospital to assess eligibility for study inclusion.

#### 6.1 Inclusion Criteria:

- Adults and children  $\geq 20 \text{ kg}$
- Symptomatic of malaria infection, i.e: history of fever within 24 hours and/or presence of fever >37.5°c.
- Microscopic confirmation of asexual stages of *P. falciparum* (mixed infection in Pailin) any parasite below 150,000/asexual per micro litre
- Ability to take oral medication.
- Written informed consent given to participate in the trial given by the patient or in case of children <16 years their attending guardian.

#### 6. Enrolment procedures

All subjects enrolled in the study will be given a unique code. A case-record form will be completed with each patient documenting symptoms prior to clinic attendance, concomitant illness, drug history. Height, weight, vital signs and physical examination findings will be recorded.

At inclusion all patients will have the following samples taken (total volume for adults  $\geq$ 16 years old: 5 ml; total volume for children under 16 years old: 3 ml).

• Malaria blood film (thick and thin) and haematocrit: 0.5ml

- Filter paper blood blots (3 dots on Whatman 3MM; approx 220-300 uL blood) for PCR parasite genotyping (msp1, msp2, glurp in case of recurrence during follow-up and polymorphism of drug resistance marker)
- Biochemistry analysis: (1 ml) (AST/ALT, bilirubin total/conjugated, alkaline phosphatase)

# **6.1 Laboratory procedures**

#### 6.1.1 Slide microscopy

Thick and thin blood films for parasite counts should be obtained and examined at screening on day 0 to confirm adherence to the inclusion and exclusion criteria. Thick blood films will be also examined on days 2, 3, 7, 14, 21, 28, 35 and 42 or on any other day if the patient returns spontaneously and parasitological reassessment is required. Specimens will be labelled anonymously (screening number or study number, day of follow-up, date).

A fresh Giemsa stain dilution will be prepared at least once a day and possibly more often, depending on the number of slides to be processed. Giemsa-stained thick and thin blood films will be examined at a magnification of 1000× to identify the parasite species and to determine the parasite density.

Three blood slides per patient will be obtained: two thick blood smears and one thin blood smear. One slide will then be stained rapidly (10% Giemsa for 10–15 min) for initial screening, while the others will be retained. If the patient is subsequently enrolled, the second slide will be stained more carefully (e.g. 2.5–3% Giemsa for 45–60 min), and slower staining will also be used for all slides obtained at follow-up visits. The study number of the patient, the date and the day of follow-up will be recorded either on the frosted edge of the slide or on the glass with a permanent glass pen.

The thick blood smear for initial screening will be used to count the numbers of asexual parasites and white blood cells in a limited number of microscopic fields.

The second blood smear will be used to calculate the parasite density, by counting the number of asexual parasites in a set number of white blood cells (typically 200) with a hand tally counter. Once a field has been started, it must be counted to completion; the final number of white blood cells will therefore rarely be exactly 200. If more than 500 parasites have been counted before 200 white blood cells have been reached, the count will be stopped after the

reading of the last field has been completed. Parasite density, expressed as the number of asexual parasites per  $\mu$ l of blood, will be calculated by dividing the number of asexual parasites by the number of white blood cells counted and then multiplying by an assumed white blood cell density (typically 6000 per  $\mu$ l).

Parasite density (per μl) = number of parasites counted × 6000 Number of leukocytes counted

The same technique will be used to establish the parasite count on each subsequent blood film. When the number of asexual parasites is less than 100 per 200 white blood cells in follow-up smears, counting will be done against at least 500 white blood cells (i.e. to completion of the field in which the 500th white blood cell is counted). A blood slide will be considered negative when examination of 1000 white blood cells reveals no asexual parasites. The presence of gametocytes on an enrolment or follow-up slide will be noted, but this information will not contribute to basic evaluation.

In addition, 100 fields of the second thick film will be examined to exclude mixed infections; in case of any doubt, the thin film will be examined for confirmation. If examination of the thin film is not conclusive, the patient will be excluded from the analysis after complete treatment and follow-up.

Two qualified microscopists will read all the slides independently, and parasite densities will be calculated by averaging the two counts. Blood smears with discordant results (differences between the two microscopists in species diagnosis, in parasite density of > 50% or in the presence of parasites) will be re-examined by a third, independent microscopist, and parasite density will be calculated by averaging the two closest counts.

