#### 13. STATISTICAL ANALYSIS:

The primary analysis will be on an 'intention to treat' basis, including all patients enrolled into the study. Primary outcome will be the Kaplan Meier analysis up to day 42 of follow-up. A per protocol analysis will be based on all enrolled patients complying with all inclusion criteria who received a full course of the study drugs. Secondary analyses include the 'adequate parasitological and clinical response' (APCR) at day 28 and day 42. Safety and tolerability measurements will be summarized for the ITT patient population.

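### Section 6.1.1 drops enrolled patients with an inconclusive thin film from an unnamed analysis, against the all-enrolled primary analysis of section 13 and, in Pailin, without an eligibility reason

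*Protocol*

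**What the plan says.** **The exclusion.** Protocol section 6.1.1 (Slide microscopy) has "100 fields of the second thick film will be examined to exclude mixed infections", with the thin film as the check in case of doubt. If that film does not settle the matter, "the patient will be excluded from the analysis after complete treatment and follow-up". No analysis set is named and no site is exempted. The patients concerned are already in the study, because the same section says: "If the patient is subsequently enrolled, the second slide will be stained more carefully".

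**The analysis sets.** Section 13 makes the primary analysis intention to treat, "including all patients enrolled into the study", with Kaplan-Meier to day 42 as the primary outcome. On the second set it says: "A per protocol analysis will be based on all enrolled patients complying with all inclusion criteria who received a full course of the study drugs".

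**Eligibility.** The inclusion criteria in section 6.1 allow "mixed infection in Pailin". The synopsis says the same in its inclusion criteria and in its primary objective, and limits the allowance to that site.

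**The forms.** The case screening form (Appendix 2) and the day-0 case report form (Appendix 3) mark a patient with any species other than *P. falciparum* as not eligible. Neither makes an exception for Pailin.

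**Outcome handling.** Appendix 5 has no row for an unresolved species reading at baseline. Its row for withdrawal and protocol violation censors the patient in the Kaplan-Meier analysis and excludes the patient from the per-protocol proportion.

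**The concern.** The protocol gives conflicting instructions for the same patient. Section 13 keeps the patient in the primary analysis and section 6.1.1 takes the patient out. If the unresolved reading is treated as a protocol violation, Appendix 5 censors the patient. The size of the primary population therefore depends on which section the analyst follows.

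The rule also ignores site. At Pursat and Battambang, where only *P. falciparum* alone is admitted, an unresolved second species is a real doubt about eligibility. In Pailin it is not. A patient there with confirmed *P. falciparum* meets the species criterion whether or not a second species is present. Read literally, section 6.1.1 keeps a clearly mixed Pailin infection and drops a possibly mixed one, although the synopsis objective covers mixed infection at that site.

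At stake are a well-defined primary population and a few evaluable patients in a sample sized closely for its target precision.

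**Working it through.** **1. The passages side by side, for an enrolled patient with an inconclusive thin film**

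| Source | Instruction |
|---|---|
| Section 13, primary analysis | Kept: all enrolled |
| Section 13, per-protocol set | Kept if inclusion criteria are met and the full course was taken |
| Section 6.1.1 | Removed from an unnamed analysis, at every site |
| Appendix 5, nearest row (protocol violation) | Kaplan-Meier: censored; per-protocol proportion: excluded |

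Two other Appendix 5 rows might seem to apply but do not. The row for infection with another species censors on the day of infection, so it concerns events during follow-up. The row for undetermined or missing PCR stands under late failures and concerns the genotyping of a recurrence.

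**2. Eligibility by site, under the synopsis and section 6.1**

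| Site | If only *P. falciparum* | If mixed | Does the doubt affect eligibility? |
|---|---|---|---|
| Pailin | admitted | admitted | No |
| Pursat, Battambang | admitted | not admitted | Yes |

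**3. The plan's own sample size (section 5)**

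Inputs: efficacy 90%, precision ±5 points, 5% dropout. The confidence level is not stated; 95% two-sided is assumed.

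- n = z² p(1 − p)/d² = 1.96² × 0.90 × 0.10 / 0.05² = 138.3. The stated 138 is reproduced.
- 138 × 1.05 = 144.9 and 138/0.95 = 145.3. The stated 145 is reproduced.

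**4. Effect on the estimate**

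The protocol gives no rate of inconclusive films. Assume e = 3 to 7 of 145 patients (3/145 = 2.1%, 7/145 = 4.8%) and 90% success among the rest. A simple proportion stands in for the Kaplan-Meier estimate. If the e patients are put back with failure rate q, the all-enrolled rate is [(145 − e) × 0.90 + e × (1 − q)]/145.

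| Failure rate q in the e patients | e = 3 | e = 7 |
|---|---|---|
| 0% | 90.2% | 90.5% |
| 10% | 90.0% | 90.0% |
| 30% | 89.6% | 89.0% |
| 100% | 88.1% | 85.7% |

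- All successes: +0.10 × e/145 = +0.2 to +0.5 points.
- All failures: −0.90 × e/145 = −1.9 to −4.3 points.

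The first and last rows are extreme bounds.

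**5. Effect on precision**

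Half-width = 1.96 × √(0.09/n).

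- n = 145: 4.88 points.
- n = 142 (3 excluded): 4.93 points.
- n = 138 (7 excluded): 5.01 points.

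**The case against.** The best defence is that section 6.1.1 was meant as a per-protocol rule. At Pursat and Battambang an unresolved species is a doubt about an inclusion criterion, section 13 already limits the per-protocol set to patients who meet those criteria, and the protocol-violation row of Appendix 5 could carry the case. That is a sensible intention, but section 6.1.1 does not say it, and it cannot explain the exclusion in Pailin.

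It can also be said that the forms make any other species ineligible everywhere, so that a Pailin patient is not eligible whichever way the film reads. The forms do say so. They conflict with the synopsis and section 6.1, which state the Pailin allowance expressly. That is a second inconsistency to reconcile and does not justify the first.

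Three stronger readings are tempting, and the protocol does not support them.

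- **Selection on outcome.** A reader might infer that patients are removed once their results are known. The trigger is a baseline film, read independently by two microscopists with a third for discordant species, and section 14 has day-0 slides validated by an expert technician. The reference to complete treatment and follow-up can simply mean that the patient's participation is not cut short. The rule is not outcome-driven by design. It remains true that the protocol does not say when the exclusion is decided, and the study is open-label.
- **A shift away from mixed infections.** A reader might infer that the rule depletes the mixed infections in the sample. It removes only unresolved films, which may be single or mixed, and keeps confirmed mixed infections in Pailin. No direction can be derived.
- **Too few patients.** A reader might infer that the exclusions alone push numbers below 138. Three to seven exclusions leave 142 to 138. The planned 5% dropout alone gives 145 × 0.95 = 137.75.

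**Conclusion.** The contradiction stands. Section 6.1.1 removes enrolled patients from an unspecified analysis while section 13 includes every enrolled patient in the primary one, and Appendix 5 does not decide between them. In Pailin the exclusion has no eligibility basis under the synopsis and section 6.1. The conflict lies in the protocol's own rules for its primary population and leaves the sample size calculation intact.

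The numerical effect is probably small. The bounds of +0.5 and −4.3 points rest on an assumed 7 affected patients who all succeed or all fail; at 30% failure among them the estimate moves by about 1 point (90.0% to 89.0%). The loss of precision is about 0.1 point. The change is worth making because it settles who is in the primary analysis at very little cost.

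**What to change.** 1. In section 6.1.1, state that patients with an inconclusive thin film stay in the primary intention-to-treat analysis.
2. Limit any exclusion for unresolved species to the per-protocol analysis or a sensitivity analysis, at Pursat and Battambang only, and decide it from the baseline slide before outcomes are reviewed.
3. State that the exclusion does not apply in Pailin.
4. Add a matching row to the Appendix 5 tables for an inconclusive baseline species reading.
5. Align the species items on the screening form and the day-0 case report form with the Pailin criterion. Otherwise the forms would still turn these patients away at enrolment.

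The cost is a sentence or two in section 6.1.1, one row in Appendix 5 and a site exception on two forms. No extra patients, visits or samples are needed.

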#### 6.1.2 Genotyping of malaria parasites

In order to differentiate a recrudescence (same parasite strain) from a newly acquired infection (different parasite strain), a genotype analysis will be conducted. This is based on the extensive genetic diversity among the malaria parasite genes *msp1*, *msp2* and *glurp*. The genotypic profiles of pre- and post-parasite strains are compared.

1

<sup>1WHO. Methods and techniques for clinical trials on antimalarial drug efficacy: genotyping to identify parasite populations. Geneva, World Health Organization, 2008 (http://www.who.int/malaria/resistance).

In addition, samples will be analysed for the presence of the Kelch 13 propeller mutation, a recently discovered molecular marker that is associated strongly with slow parasite clearance and in vitro artemisinin resistance using the Ring Survival Assay (RSA).

The copy number of *P. falciparum* mdr1 gene will also be measured. An increasing copy number is associated with mefloquine (MQ) resistance and treatment failures with ASMQ.

In order to minimize discomfort to the patient due to repeated finger pricks, two to three drops of blood will be collected on filter paper Whatman 3MM during screening or enrolment and each time blood smears are required according to the protocol on and after day 7. Specimens will be labeled anonymously (study number, day of follow-up, date), kept in individual plastic bags with desiccant pouches and protected from light, humidity and extreme temperature until analyzed. When such room temperature conditions are not possible, for example in extremely humid environments where air-conditioning is not available, storage in a refrigerator or freezer will be considered, but great care will be taken to protect samples from frost and moisture. The PCR technique used will be performed by laboratory of Institut Pasteur in Cambodia. Paired filter papers will be used for parasite DNA extraction and genotyping. Unused filter papers will be kept in safe locations until data are eventually validated or for further research needs.

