#### 3. Study endpoints

The primary endpoint of the study is D28 PCR and D42 PCR corrected ACPR to assess therapeutic efficacy pyronaridine artesunate for the treatment of uncomplicated falciparum malaria in an area where artemisinin resistant malaria is prevalent.

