#### 14. Quality assurance/quality control procedures

All blood slides from day 0, 3, 7, 21, 28, 42 and those from any return day will be validated by a CNM expert-level technician and also.

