Possible Hy's Law case following the FDA Guidance on Drug Induced Liver Injury: Premarketing Clinical Evaluation dated July 2009 A possible Hy's law case is defined as a subject with any value of ALT or AST above 3xULN together with an increase in bilirubin to a value higher than 2xULN and NOT associated to an ALP value higher than 2xULNA decision on medical and scientific grounds is required to assess whether an immediate notification of an event is warranted in other situations, such as medically important events which are not life-threatening, fatal or cause hospitalization, but could endanger the patient or could rendered necessary an intervention to prevent one of the above conditions to develop.

Remark: Examples of such events are intensive care in the emergency room or at home to treat a bronchospasm; a haematological dyscrasia; convulsions or an asymptomatic increase ALT ( $\geq 10 \text{ x ULN}$ ) not causing hospitalisation, or the development of drug addiction or abuse

TABLE 1: STUDY SCHEDULE

	D0	D1	D2	D3	D4	D7	D14	D21	D28	D35	D42	REPf		olumes
Screening													(ml) per time	
Written informed consent	X												adult	Child
Assign participant ID	X												≥16 yrs	<16yrs
Participant's history	X													
Symptoms checklist	X	X	X	X	X	X	X	X	X	X	X	X		
Vital signs	X	X	X	X	X	X	X	X	X	X	X	X		
Temperature	X	X	X	X	X	X	X	X	X	X	X	X		
General Examination	X	X	X	X	X	X	X	X	X	X	X	X		
Study Drug administration														
PYR-Artesunate	X	X	X											
Laboratory Procedures														
#Malaria blood film	X	X	X	X	X	X	X	X	X	X	X	X	0.5	0.5
HCT or Hb	X	X	X	X	X	X	X	X	X	X	X	X	0.03	0.03
Filter paper blots	X											X	0.3	0.3
FBC	X			X		X	X		X		X	X	1	1
Biochemistry	X			X	_	X	X		X		X	X	1	1
	X					X						X	0.5	0.5

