# APPENDIX 5. GUIDELINES FOR ANALYSIS OF RESULTS

	PCR-uncorr	ected results
End-point for day X (X = 28 or 42)	Cumulative success or failure rate (Kaplan-Meier analysis)	Proportion (per-protocol analysis)
Adequate clinical and parasitological response on day X	Success	Success
Early treatment failure	Failure	Failure
Late clinical failure before day 7	Failure	Failure
Late clinical failure or late parasitological failure on or after day 7	Failure	Failure
Other species infection	Censored day of infection	Excluded from analysis
Lost to follow-up	Censored last day of follow-up according to timetable	Excluded from analysis
Withdrawal and protocol violation	Censored last day of follow-up according to timetable before withdrawal or protocol violation	Excluded from analysis

	PCR-correcte	d results
End-point for day X (X = 28 or 42)	Cumulative success or failure rate (Kaplan-Meier analysis)	Proportion (per-protocol analysis)
Adequate clinical and parasitological response at day X	Success	Success
Early treatment failure	Failure	Failure
Late clinical failure before day 7	Failure	Failure
Late clinical failure or late parasitological failure on or after day 7		
falciparum recrudescence*	Failure	Failure

 
falciparum reinfection*
 
	Censored day of reinfection	Excluded from analysis
other species mixed with falciparum recrudescence	Failure	Failure
other species mixed with falciparum reinfection	Censored day of reinfection	Excluded from analysis

 
other species infection
 
	Censored day of infection	Excluded from analysis

 
undetermined or missing PCR
 
	Excluded from analysis	Excluded from analysis
Lost to follow-up	Censored last day of follow- up according to timetable	Excluded from analysis
Withdrawal and protocol violation	Censored last day of follow- up according to timetable before protocol violation or withdrawal	Excluded from analysis

\* WHO. Methods and techniques for clinical trials on antimalarial drug efficacy: genotyping to identify parasite populations. Geneva, World Health Organization, 2008 (http://www.who.int/malaria/resistance).

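### Table 1 leaves out the filter-paper blots that section 6.1.2 and the CRFs call for from day 7, so a recrudescence confirmed after its visit can drop out of the PCR-corrected endpoint

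*Protocol*

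**What the plan says.** Three parts of the protocol say when blood for genotyping is taken.

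- **Section 6.1.2** requires it on "filter paper Whatman 3MM during screening or enrolment and each time blood smears are required according to the protocol on and after day 7".
- **The follow-up CRFs** (Appendix 3) for days 7, 14, 21, 28 and 35, for unscheduled days and for the final day each ask whether a PCR blood sample was taken.
- **Table 1 (Study schedule)** has a row "Filter paper blots" marked under D0 and REP only. The row "Malaria blood film" in the same table is marked at every visit from D0 to D42 and at REP.

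Four other provisions make the difference matter.

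- Section 3: "The primary endpoint of the study is D28 PCR and D42 PCR corrected ACPR".
- Section 6.1.2: "Paired filter papers will be used for parasite DNA extraction and genotyping".
- Section 6.1.1 has two microscopists read every slide independently. Slides on which they disagree, including on whether parasites are present, "will be re-examined by a third, independent microscopist". Section 14 lists slides from days 0, 3, 7, 21, 28 and 42 for validation and adds that "those from any return day will be validated by a CNM expert-level technician".
- Appendix 5, in its PCR-corrected table, excludes "undetermined or missing PCR" from both the Kaplan-Meier analysis and the per-protocol proportion.

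**The concern.** Recrudescence and reinfection can be separated only if there is a blot from day 0 and another from the day of recurrence. Section 6.1.2 secures the second blot whatever the film shows. Table 1 takes it only once a recurrence has been recognised. If a film is first read as negative and later called positive, a site that followed Table 1 has no blot from that visit.

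Missing PCR arises only in patients with a recurrence, so the exclusion is not neutral. Where the recurrence was a recrudescence, a treatment failure leaves the analysis and estimated efficacy rises. Section 1 says the study is meant to find out whether the 10% day-42 recrudescence seen earlier at the western Cambodian site was real, so a loss in this direction would work against its purpose. A blot that was never taken cannot be recovered at analysis.

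**Working it through.** **1. Is the gap in Table 1 real?** Aligned with the column heads, the filter-paper row has marks at D0 and REP and empty cells from D1 to D42. The full blood count and biochemistry rows, aligned the same way, give D0, D3, D7, D14, D28 and D42, which is what section 9 states. The table therefore reads correctly and the blanks are not a conversion fault. A last row whose label is not legible is marked at D0, D7 and REP. Even if it were a second PCR sample, D14 to D42 would stay blank.

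**2. Which visits differ?** Films are required at D7, D14, D21, D28, D35 and D42. Section 6.1.2 attaches a blot to all six; Table 1 attaches it to none.

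**3. Can a film become positive after the visit?** The protocol gives no time for the third reading or for the expert validation, so this is an inference. It is a reasonable one: follow-up slides get the slower stain (45 to 60 minutes is the example in section 6.1.1), then two independent readings, then a third if the two disagree, and those from the listed days are also validated. A recurrence missed at D7 to D35 and left untreated meets another scheduled film one or two weeks later. After D42 there is none, and no rule for recalling and resampling the patient is stated.

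**4. The plan's own figure.** Section 5 gives an assumed efficacy of 90%, precision of ±5 points, 138 patients, and 145 after 5% dropout. With 95% two-sided confidence (assumed, since the level is not stated):

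n = 1.96² × 0.90 × 0.10 / 0.05² = 138.3, and 138 × 1.05 = 144.9.

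Both figures reproduce, and this point does not affect them.

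**5. Effect of each lost recrudescence.** Take 138 evaluable patients. At 10% failure, 13.8 rounds to 14 recrudescences and leaves 124 successes. If k recrudescences have no paired blot and are excluded,

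efficacy = 124 / (138 − k).

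| k | Calculation | Efficacy |
|---|---|---|
| 0 | 124/138 | 89.9% |
| 1 | 124/137 | 90.5% |
| 3 | 124/135 | 91.9% |
| 5 | 124/133 | 93.2% |
| 7 | 124/131 | 94.7% |

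The first loss adds about 0.7 points, and later ones slightly more. Without other censoring, the Kaplan-Meier estimate at day 42 equals this proportion, so the same figures serve for both analyses. The values of k are assumptions; the documents give none.

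**6. Lost reinfections.** In the per-protocol proportion, Appendix 5 excludes reinfections anyway, so losing their PCR changes nothing. In Kaplan-Meier they would be censored on the day of reinfection. Excluding them outright instead shrinks the risk set and, if anything, lowers the estimate slightly. The upward shift comes only from lost recrudescences.

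**The case against.** The strongest reply is that the protocol already shows its intention. Section 6.1.2 is the detailed procedure, and staff meet the PCR question on the CRF at every scheduled visit from day 7. Harm requires a site to follow a summary table against both. It also requires a film to be read negative first and positive later, and no blot to be taken in between. A film recognised as positive at the visit falls under REP, where Table 1 does mark a blot. A patient recalled while still parasitaemic and untreated could be sampled the same way.

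Most of this stands, and it limits the likely number of lost pairs. It does not remove the conflict: section 9 refers staff to Table 1 for follow-up, and D42 has no later scheduled film to fall back on.

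A reader might go further and infer that the primary endpoint will lose failures, or that the whole ±5-point margin is at risk. The documents support neither. Loss is possible but not certain. The larger shifts, such as 94.7% with seven lost, require half of all recrudescences to be misread at first and never resampled, and nothing in the protocol suggests that rate. Nor does every missing pair raise the estimate, since a lost reinfection does not.

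**Conclusion.** The contradiction is clear: Table 1 disagrees with section 6.1.2 and with the CRFs at six scheduled visits. Combined with the Appendix 5 exclusion, it can bias PCR-corrected efficacy upward by about 0.7 points per lost recrudescence, assuming 138 evaluable patients and 14 recrudescences. The total cannot be computed, because the protocol does not say how often a film is called positive after the visit or how often such a patient is resampled. D42 carries the greatest risk. The point should be corrected because it touches the primary endpoint and the remedy is cheap, not because a large bias has been shown.

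**What to change.** In Table 1, mark the filter-paper row at D7, D14, D21, D28, D35 and D42 in addition to D0 and REP, so that it agrees with section 6.1.2 and the follow-up CRFs.

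The cost is filter paper and storage, plus 0.3 ml of blood at each added visit: 6 × 0.3 = 1.8 ml per patient over follow-up. Blood is already drawn for the film at each of these visits. The volume columns in Table 1 are per time point and already show 0.3 ml for this row, so they need no change. The correction has to be in place before sampling starts.
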